Contralaterally Controlled FES plus Video Games for Hand Therapy after Stroke

NCT03058796

Study Protocol and Statistical Analysis Plan

Note: The text below was extracted from the IRB protocol for this study, which was first approved on February 9, 2017. The most recent amendment to the protocol was approved on:

August 8, 2019

Study Protocol

Abstract

Objectives: This study will determine the effect of integrating two promising therapy modalities for improving upper limb function after stroke, hand therapy video games (HTVG) and contralaterally controlled functional electrical stimulation (CCFES). It is expected that CCFES+HTVG will enhance the motor impairment and functional outcomes achieved by CCFES alone. Secondarily, we will evaluate the effect of baseline impairment and time post-stroke on treatment response, and explore the effects of CCFES+HTVG vs. CCFES alone on cortical activity during a hand task (fMRI assessment).

Research Plan: This is a randomized controlled trial in which stroke patients will be assigned to either CCFES+HTVG or CCFES for 12 weeks. Hand dexterity, upper limb impairment, and upper extremity activity limitation will be evaluated by a blinded assessor at 0 (baseline), 3, 6, 9, 12 (end of treatment), 24, and 36 weeks. Cortical activation will be assessed at 0 and 12 weeks.

Methodology: Up to 52 stroke survivors with chronic (> 6 months) upper extremity hemiplegia will be enrolled and randomized. The two groups will receive equivalent doses of treatment over a 12 week period consisting of 10 sessions per week (7.5 hrs) of self-administered treatment at home plus 2 sessions per week (3 hrs) of group-specific occupational therapy in the lab. The home sessions for the CCFES+HTVG group will consist of CCFES-mediated video game play according to instructions provided during the lab sessions. For the CCFES group, the home sessions will consist of CCFES-mediated hand opening exercise. The lab sessions for both groups will consist of a period of observation and instruction regarding the home sessions followed by CCFES-mediated functional hand task practice.

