Clinical Significance: This study will demonstrate the supplemental motor relearning value of virtual reality/video games to CCFES therapy, (2) identify patients most likely to respond to both therapies, and (3) determine whether adding HTVG to CCFES simply enhances cortical activation underlying CCFES or engages additional cortical areas to improve response across broader ranges of severity and chronicity. This study is an important step toward the development and dissemination of new

treatments that may be applicable and effective across a wide range of patients who have lost hand function after stroke.

Specific Aims

AIM 1: Determine the effect of integrating Hand Therapy Video Games (HTVG) with Contralaterally Controlled Functional Electrical Stimulation (CCFES) on upper extremity motor outcomes

Hypothesis 1: Stroke patients treated with CCFES+HTVG will have greater and faster improvements in hand dexterity, upper limb impairment, and activity limitation than those treated with CCFES alone

AIM 2: Evaluate the effect of baseline impairment and time post-stroke on treatment response

Hypothesis 2: Compared to CCFES, CCFES+HTVG will benefit patients with greater baseline impairment and time elapsed post-stroke.

AIM 3: Explore the effects of CCFES+HTVG vs. CCFES on cortical activation during a hand task

Hypothesis 3: Compared to CCFES, CCFES+HTVG will exhibit greater re-mapping in the brain, demonstrated as greater lateralization of activity, greater recruitment of learning- based networks in ipsilesional and contralesional regions, and increased intensity of cortical activity.

Methods and Procedures

General Study Design

A single-blinded randomized controlled trial will be carried out to assess the effects of 12 weeks of CCFES+HTVG compared to CCFES. Dexterity, upper limb impairment, and activity limitation will be assessed at 0 (baseline), 3, 6, 9, 12 (end of treatment), 24, and 36 wks. Cortical activation (measured with fMRI) will be optionally assessed at 0 and 12 wks. The treatment dose will be the same for both groups: 10 sessions per week (7.5 hrs) of self-administered treatment at home plus 2 sessions per week (3 hrs) of group-specific occupational therapy in the lab.

Device

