Stimulation is delivered through standard self-adhering pre-gelled 2"x2" square and 1.25" round electrodes (e.g., PALS®, Axelgaard Manufacturing, Fallbrook, CA). The analog input source for the stimulator is an assembly of three passive bend sensors 1/4" wide by 4 1/2 " long (Spectra Symbol, Salt

Lake City, UT) which are either attached by Velcro or inserted through slits cut into the top of the index, middle, and ring fingers of an athletic glove.³ The sensors act as variable resistors. When the fingers open and close, the electrical impedance of each sensors changes; these impedance changes are supplied as the analog input to the stimulator. The stimulator is programmed to produce current pulses with pulse widths (intensities) that are proportional to input from the glove worn on the nonparetic hand.

The CCFES+HTVG system uses a bend sensor that is worn on a finger of the paretic hand to detect opening and closing. The sensor is attached to a fingerless “glove” and plugs into an analog-to-digital converter module, which in turn plugs into a USB port on a 17-inch touchscreen laptop computer. The computer is an all-in-one unit that requires no other components besides the monitor’s touchscreen (no keyboard or mouse) to select and play the games. The computer is configured so that it can only be used for the game play prescribed to the participant and requires a USB key from the investigators to run.

Randomization

Subjects will be assigned to a treatment group using an adaptive randomization algorithm⁵ to minimize group imbalances on 4 key patient characteristics: (1) time post-stroke (< 2 yrs vs. \geq 2 yrs), (2) baseline motor status (moderate vs. severe), (3) paretic side (dominant vs. non-dominant),⁶ and (4) fMRI eligibility (yes vs. no). Patients with $\geq 10^\circ$ active wrist extension, 10° active thumb abduction/extension, and 10° active extension in at least two additional digits will be considered to have “moderate” impairment, and patients with less movement than that who meet all the other motor criteria (see Section 30) will be considered to have “severe” impairment.⁷

Device Set Up

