We will enroll only patients who are no longer receiving rehabilitation therapies to the upper limbs. The use of electrical stimulation or other experimental rehabilitation techniques involving the hemiparetic upper limb, changes in spasticity medications, botulinum toxin injections to upper limb muscles, use of an arm sling, and use of a resting hand splint will be discouraged unless it is deemed medically necessary. To account for the potential confounding effect of such concomitant therapies, all concomitant therapies will be documented and any group imbalance will be accounted for in the statistical analysis.

Upper Limb Motor Assessments

All subjects will undergo assessments of hand dexterity (BBT), upper limb impairment (UEFM, Maximum Voluntary Finger and Elbow Extension and Tracking), activity limitation (AMAT) by a blinded assessor at 0 (baseline), 3, 6, 9, 12 (end of treatment), 24, and 36 wks. All assessments will be done with no electrical stimulation. Subjects will refrain from using their stimulators for 24 hours prior to their 3, 6, 9, and 12 week assessments in order to avoid any transient carry-over effect or muscle fatigue.

Box and Blocks Test (primary)

The BBT is a measure of gross manual dexterity, which requires the subject to pick up one block at a time, move it over a partition, and release it in a target area as many times as possible in a 60-sec period.

Upper Extremity Fugl-Meyer Assessment

The UEFM is a measure of post-stroke upper limb motor impairment. The assessor requests the subject to attempt specific volitional movement of the upper limb (shoulder, elbow, forearm, wrist, and hand), and rates their ability to perform each movement using a 3-point ordinal scale (0, cannot perform; 1, perform partially; and 2, perform fully). The maximum score is 66.

Arm Motor Abilities Test

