- Electrical stimulation should not be used by patients with implanted electronic devices (cardiac demand pacemakers etc.) unless under specialized medical supervision.
- Do not participate in this study if you have a history of potentially fatal cardiac arrhythmias.
- Electrical stimulation should not be used by people who have poorly controlled epilepsy.
- The stimulator has been programmed specifically for the intended user only. Do not let others use the stimulator.

Statistical Analysis Plan

We hypothesize that the CCFES+HTVG group will have greater post-treatment gains than the CCFES group on upper extremity motor outcomes. Exploratory looks at the data will be done before fitting our models. The adaptive randomization should force relatively good balance of potential confounding variables (e.g., fMRI eligible, severity of impairment, time post-stroke), but imbalances in treatment adherence or any other baseline covariate (e.g., lesion location, etc.) or adherence may still require their inclusion as covariates. Each measure will be modeled using a linear mixed effects approach which is well-suited for handling correlated repeated measurements, unbalanced data, and missing data and dropouts in longitudinal studies, while permitting us to control for potential confounders.¹ Least square (LS) means will be calculated using model estimates and adjusted for missing values for each group at each time point. This approach allows comparisons and estimates of treatment group effects at any time point, and also allows comparisons and estimates across time points within groups to evaluate the persistence or decay of the treatment effect. Secondarily, we hypothesized that participants who were less than 2 years after stroke or had moderate hand impairment at baseline would improve more than participants who were more than 2 years after stroke or had severe hand impairment at baseline. A mixed effects modeling analysis will be used similar to the primary analysis to evaluate the effects of time post-stroke and impairment severity. For fMRI data, differences from baseline to EOT in beta coefficient maps for each region of interest will be evaluated with paired t-tests and cluster threshold set to >100 voxels. Between-group comparisons will be made with independent t-tests.

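### The SAP contains no test of Hypothesis 2: its secondary hypothesis ignores treatment arm, and no treatment-by-severity or treatment-by-chronicity contrast is specified

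*Combined protocol and SAP*

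**What the plan says.** Specific Aims, Aim 2, is to "Evaluate the effect of baseline impairment and time post-stroke on treatment response". The Abstract describes the same aim as secondary. The hypothesis under that aim is a comparison of arms: "Compared to CCFES, CCFES+HTVG will benefit patients with greater baseline impairment and time elapsed post-stroke".

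The Statistical Analysis Plan states one secondary hypothesis, that "participants who were less than 2 years after stroke or had moderate hand impairment at baseline would improve more than participants" who were later after stroke or had severe impairment. It gives the method in one sentence: "A mixed effects modeling analysis will be used similar to the primary analysis to evaluate the effects of time post-stroke and impairment severity". For the primary model it says "This approach allows comparisons and estimates of treatment group effects at any time point", and it adds comparisons across time points within groups. Elsewhere in the plan, severity and time post-stroke appear only as possible confounders that the adaptive randomization should balance.

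The Randomization section already defines both factors in two categories (under 2 years against 2 years or more; moderate against severe). The Upper Limb Motor Assessments section labels the Box and Blocks Test as primary.

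**The concern.** The two sections ask different questions. Hypothesis 2 asks about the effect of adding the games in severe or late patients. The SAP asks whether moderate or early patients gain more than severe or late ones, whichever treatment they had. Both statements can be true together, and either can be true without the other.

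Hypothesis 2 is itself ambiguous. It may mean (a) that the games have an effect within severe or late patients, or (b) that the effect is larger there than in moderate or early patients. The SAP specifies a test of neither.

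Two things are at stake. First, the arm-free result could be reported under Aim 2 as if it bore on Hypothesis 2. Second, any comparison of arms by severity or chronicity would have its model term, outcome and visit chosen after the data are seen, from several measures at six post-baseline visits.

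**Working it through.** **Text check.** There is no stated figure to reproduce, because the documents give no analysis for Hypothesis 2.

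| | Specific Aims, Hypothesis 2 | SAP, secondary hypothesis |
|---|---|---|
| Groups compared | CCFES+HTVG against CCFES | Early or moderate against late or severe |
| Role of severity and chronicity | Define where the treatment effect is sought | Are themselves the effects studied |
| Quantity needed | Arm contrast in a stratum, or its difference between strata | Stratum difference, arms pooled |

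**What the arm-free contrast contains.** Let m and s be mean gains in moderate and severe patients, with C for CCFES and G for CCFES+HTVG. Assume 1:1 arms within each stratum (the allocation ratio is not stated).

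- Arm-free contrast: A = (mC + mG)/2 − (sC + sG)/2
- Interaction: I = (sG − sC) − (mG − mC)
- Rearranged: A = (mC − sC) − I/2

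The gap under CCFES alone, mC − sC, is unknown, so A is one result for two unknowns. Adding arm as a main effect does not help: with balanced arms, A is unchanged and I is still not estimated.

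Four sets of assumed gains (illustrative, not from the documents):

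| Case | CCFES m/s | Games m/s | A | Games effect in severe, reading (a) | I, reading (b) |
|---|---|---|---|---|---|
| 1 | 6 / 2 | 6 / 5 | 4 − 1.5 = 2.5 | +3 | +3 |
| 2 | 6 / 3.5 | 6 / 3.5 | 2.5 − 0 = 2.5 | 0 | 0 |
| 3 | 6 / 5 | 6 / 2 | 1 + 1.5 = 2.5 | −3 | −3 |
| 4 | 4.5 / 2 | 7.5 / 5 | 2.5 − 0 = 2.5 | +3 | 0 |

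Hypothesis 2 is true on both readings in case 1, false on both in case 2, reversed in case 3, and true only on reading (a) in case 4. The planned contrast is the same in all four.

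**Precision of the missing analysis.** The documents give up to 52 patients but no SD, alpha, power, severity split or dropout. Assumed: two-sided 5%, 80% power, 1:1 arms, one visit, and results in units of the within-cell SD of the analysed outcome. With n patients per arm and a proportion p severe:

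- SE of the interaction = √[2/(np) + 2/(n(1−p))]
- SE of the severe-stratum contrast = √[2/(np)]
- Detectable difference = (1.960 + 0.842) × SE

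For 52 patients and equal strata (13 per cell), the interaction SE is √(4/13) = 0.555. The detectable difference is 2.802 × 0.555 = 1.55 SD (1.59 with the noncentral t on 48 df), and the 95% CI half-width is 2.011 × 0.555 = 1.12 SD. The severe-stratum SE is √(2/13) = 0.392, which gives 1.10 SD detectable and a half-width of 0.79 SD.

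| Patients with data | Share severe | Interaction SE | Detectable interaction (SD) | Severe-stratum SE | Detectable contrast (SD) |
|---|---|---|---|---|---|
| 52 | 1/2 | 0.555 | 1.55 | 0.392 | 1.10 |
| 52 | 1/3 | 0.588 | 1.65 | 0.480 | 1.35 |
| 52 | 1/4 | 0.641 | 1.79 | 0.555 | 1.55 |
| 44 (about 15% lost) | 1/2 | 0.603 | 1.69 | 0.426 | 1.19 |
| 44 | 1/3 | 0.640 | 1.79 | 0.522 | 1.46 |
| 44 | 1/4 | 0.696 | 1.95 | 0.603 | 1.69 |

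For comparison, the overall arm effect at 52 patients has SE √(2/26) = 0.277 and is detectable at 0.78 SD. The arm-free contrast with equal strata has the same precision. The interaction SE is twice as large.

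**The case against.** The best defence is that the secondary model is described as resembling the primary one, which is built around treatment group. Such a model might keep arm and yield arm contrasts by stratum. That is possible, but the text does not say so. The primary contrasts are by time point, and the named target is the effects of the two factors, not their interaction with arm. A prespecified test should not have to be inferred.

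A second point is that Aim 2 can be read as prognostic, and the Clinical Significance paragraph speaks of finding patients likely to respond to both therapies. This stands: the SAP does serve that reading. But Hypothesis 2 is explicitly between arms, and the same paragraph also asks whether adding games improves response across broader ranges of severity and chronicity.

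Third, Hypothesis 2 and the stratum cut-points are fixed in advance, so a later arm comparison in those strata would not be wholly post hoc. This also stands in part: the model term, outcome and visit would still be open.

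Fourth, the public text is an extract from a longer protocol, so absence is shown only for this document. The SAP section nevertheless reads as continuous.

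Finally, the precision figures rest on assumptions, and baseline adjustment or use of repeated visits could improve precision. The finding does not depend on those figures.

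**Conclusion.** The concern holds. The SAP states an analysis that answers a different question from Hypothesis 2, and nothing else in the document supplies the missing contrast. One of three numbered hypotheses has no specified test on either reading. This should be fixed. It is not critical, because the primary comparison of arms is unaffected and the prognostic reading of Aim 2 is served.

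That conclusion rests on the text alone. The identity behind the four cases needs only balanced arms within strata; the gains in them are invented to show that the planned result does not identify the treatment effect in severe patients. The detectable interaction of about 1.55 to 1.95 SD depends on the assumed sample, severity split, alpha and power. It shows that the corrected analysis can only be exploratory.

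**What to change.** - State Hypothesis 2 in the same words in the Specific Aims and the SAP, and say whether it means (a) benefit within severe or late patients or (b) greater benefit there than in moderate or early patients.
- For the Box and Blocks Test at one named visit (for example 12 weeks, end of treatment), prespecify the treatment-by-severity and treatment-by-time-post-stroke interactions, one factor per model, using the randomization categories.
- Report each interaction and the stratum-specific treatment contrasts with 95% confidence intervals, all labelled exploratory.
- Keep the present early/moderate comparison as a separately labelled prognostic analysis.

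The single outcome, single visit and two-category factors are choices made to limit the number of comparisons and to use what is already recorded. Others would serve if fixed in advance.

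The cost is SAP wording and two single-degree-of-freedom interactions with their stratum contrasts; no new assessments or patients are needed. The downside is imprecision: with a 95% CI of about ±1.12 SD for the interaction even with equal strata and no dropout, the report must say that a null result does not refute Hypothesis 2.

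### The SAP words Aim 2 as two-level contrasts and names no treatment-by-baseline interaction, although Hypothesis 2 is graded and concerns the differential benefit of CCFES+HTVG.

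*Combined protocol and SAP*

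**What the plan says.** The Specific Aims state Aim 2 as: "Evaluate the effect of baseline impairment and time post-stroke on treatment response". Hypothesis 2 is comparative and graded. Relative to CCFES alone, "CCFES+HTVG will benefit patients with greater baseline impairment and time elapsed post-stroke". It gives no cut-point.

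The Statistical Analysis Plan words the secondary hypothesis differently. It expects that "participants who were less than 2 years after stroke or had moderate hand impairment at baseline would improve more" than those beyond 2 years or with severe impairment. The model follows in one sentence: "A mixed effects modeling analysis will be used similar to the primary analysis to evaluate the effects of time post-stroke and impairment severity". That sentence gives neither the coding of the two factors nor an interaction with treatment group.

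The two divisions match two of the four minimisation factors in the Randomization section. There, impairment is classed by a movement rule: patients with at least 10° of wrist extension, 10° at the thumb and 10° of "active extension in at least two additional digits will be considered to have" moderate impairment. Those with less movement who meet the other motor criteria are classed as severe.

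Graded information is also collected. Time post-stroke is listed under Baseline Variables. The UEFM (maximum 66) and maximum finger extension in degrees are both assessed at week 0. On size: "Up to 52 stroke survivors with chronic (> 6 months) upper extremity hemiplegia will be enrolled and randomized".

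**The concern.** There are two problems, and the first is the larger.

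**The estimand.** Hypothesis 2 is about effect modification: does the difference between arms change with impairment or time since stroke? The SAP hypothesis is about prognosis: do some participants improve more than others, whichever arm they are in? A model with main effects of time post-stroke and severity answers the second question and says nothing about the first.

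**The coding.** Strata that serve to balance the arms appear to be carried over as the analysis variables. A 2-year split treats a patient at 7 months like one at 23 months, and a patient at 25 months like one many years out. If response changes gradually, that variation is lost, and interactions are already imprecise at this sample size. If the coding is instead still open, it could be settled after the exploratory looks that the SAP schedules before model fitting.

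At stake is one of the trial's three stated contributions, identifying the patients most likely to respond.

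**Working it through.** The documents give no alpha, power, SD, effect size or moderator distribution, so there is no planned figure to reproduce. The inputs are N = 52 (Abstract), about 26 per arm if balanced, and the 2-year cut. Everything else below is an assumption. Two-sided alpha 0.05 and 80% power are used where needed.

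**Step 1: how demanding the interaction is.** Take a single-time-point comparison in residual SD units, with 1.960 + 0.842 = 2.802.
- Two-arm contrast, 26 v 26: 2.802 × √(2/26) = 0.78 SD.
- 2×2 interaction, 13 per cell (the most favourable split): 2.802 × √(4/13) = 1.55 SD.

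The interaction must be twice as large as a simple contrast to be detected.

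**Step 2: information kept by a split of a normal moderator.** With a linear effect, the fraction kept is the squared correlation between the moderator and its split, φ(z)² / [p(1 − p)], where p is the share below the cut. It carries over to the interaction slope if the moderator has the same distribution in both arms.

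| Split | Fraction kept | Loss | 52 × fraction |
|---|---|---|---|
| 50/50 | 0.1592 / 0.25 = 0.637 | 36.3% | 33.1 |
| 70/30 | 0.1209 / 0.21 = 0.576 | 42.4% | 29.9 |
| 80/20 | 0.0784 / 0.16 = 0.490 | 51.0% | 25.5 |

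For a normal moderator 36.3% is the smallest possible loss. As an illustration, if the continuous analysis had 80% power, the median split would have Φ(2.802 × √0.637 − 1.960) = 61% and the 70/30 split 57%.

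**Step 3: other shapes.**
- Uniform moderator: fraction kept is 3p(1 − p), so the loss is 25% at the median, 37% at 70/30 and 52% at 80/20.
- Two equal normal clusters split midway: loss of 32% at 2 SD separation and 25% at 3 SD.
- Skewed time, simulated as 0.5 years plus a log-normal variable (median time 1.5 to 4.5 years, log-SD 0.8 or 1.0) and cut at 2 years: loss of 34% to 69% if the effect is linear in log time, and 50% to 92% if linear in time itself. The share under 2 years ran from 69% down to 11%.
- True step exactly at the cut: no loss.

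**Step 4: impairment.** The formula in Step 2 does not apply here. Moderate/severe is a multi-joint movement rule, not a cut on the UEFM or on finger extension. If the scale underlying the rule correlated 0.7 to 0.9 with the UEFM (assumed), an even split would keep ρ² × 0.637 = 31% to 52% of the UEFM information. That shows mainly that the two are different constructs.

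**The case against.** The case on the other side is substantial.

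- **The coding is not stated.** A reader might infer that the SAP commits the model to two-level predictors. It does not. The hypothesis is two-level, the model sentence is silent, and Aim 2 itself is worded as a gradient. This stands: two-level coding is implied, and it is the natural reading, but no more.
- **The loss is conditional.** A reader might infer that over a third of the information is certain to be lost. The documents give no distribution, split or shape of effect, and eligibility truncates time at 6 months. This stands; the figure has to be given as a range.
- **Impairment is not a dichotomised score.** A reader might take moderate/severe to be a split UEFM. The Randomization section shows that it is not, and the UEFM also covers the shoulder and elbow. Replacing the label with the UEFM changes the question somewhat. It also couples moderator and outcome when the UEFM is the response. Both points stand, and the fix has to deal with them.
- **The cuts are prespecified.** Using minimisation factors in the analysis is ordinary practice, and the impairment rule carries a citation, so it cannot be called arbitrary from the documents alone. No rationale is given for 2 years. But prespecification guards against a data-driven choice of cut; it does not recover lost information.
- **The aim is secondary.** This is true, and the primary comparison is unaffected.

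A reader might also infer that the SAP and Hypothesis 2 contradict each other in direction. They need not. Milder or more recent cases could improve more overall while the added benefit of HTVG is larger in the others. The two statements concern different quantities, and that is why the interaction must be named.

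**Conclusion.** The point holds in a limited form. The missing treatment-by-baseline interaction can be read directly from the SAP and is the main gap: without it, Hypothesis 2 is not tested. The two-level coding is implied rather than stated.

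For time post-stroke, a split would cost about 36% to 51% of the information if log time is roughly normal with a linear effect and the split lies between 50/50 and 80/20. The loss is smaller under some other shapes (25% for a uniform moderator at the median, none for a step at the cut) and larger for strongly skewed time. Nothing in the documents argues for a step at 2 years. For impairment, no loss figure can be derived from the documents.

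This is a change the sponsor should make to a secondary analysis. Continuous coding will not make Aim 2 well powered with 52 participants. It avoids a loss that the trial can ill afford, and the interaction makes the estimate answer the stated question.

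**What to change.** Revise the Aim 2 paragraph of the SAP as follows.

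1. **Time post-stroke.** Enter log(time post-stroke) as a continuous variable in the mixed model, with its interaction with treatment group and with assessment time. Report the treatment interaction with a 95% CI, and the predicted treatment effect at a few prespecified values of time since stroke.
2. **Impairment.** Specify the treatment interaction and name one graded baseline measure already collected, such as finger extension in degrees or the UEFM, as the moderator. State that it is not the same construct as the moderate/severe rule. Where that measure is also the outcome, its week-0 value must not serve as both response and moderator: use the other measure, or model post-baseline values only.
3. **Two-level contrasts.** Keep them as supportive, also with their treatment interactions.
4. **Timing.** Fix the coding before any exploratory look at outcome data.

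The cost is SAP wording, with no new assessments, provided that time post-stroke is recorded more finely than the stratum. The documents do not give its scale, so this should be confirmed. The downsides are an assumption of approximate linearity, to be checked with a plot, and a slightly different impairment construct from the one used in randomisation.
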